### 1. PURPOSE.

This research study is intended to 1) better understand seriously ill adults' and their family care partners' (FCP), particularly persons living with dementia (PLwD), barriers to accepting community-based palliative care (CBPC); 2) develop an intervention to address barriers; and 3) pilot test whether the intervention has an impact on CBPC uptake among patients who previously refused CBPC. The intervention will consist of 1) a set of informational material describing the benefits of CBPC for the CBPC team to use when presenting CBPC to VNS Health Total (formerly VNS Choice) members and FCP; and 2) processes for tailoring information delivery so that eligible members and their FCP receive information about CBPC that is tailored to their individualized risk as identified by VNS Health's validated 12-month mortality risk algorithm.

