### 2. SPECIFIC AIMS.

The specific Aims of the study are:

**Aim 1:** Engage FCPs and CBPC team members to identify barriers to CBPC. Aim 1 will incorporate the perspectives of 10 CBPC team members and 25 VNS Health Total members and FCPs of PLwD and those with other diagnoses who refused CBPC services.

**Aim 2:** Develop informational materials for CBPC team members to use when speaking with patients and FCPs about CBPC and process for tailoring information delivery based on patient's algorithm-identified risk profile. 10-15 persons from interested parties (CBPC team members, FCPs, content/research experts) will provide feedback on intervention materials. Most participants will be recruited from Aim 1 participants. Additional participants will be recruited as necessary.

**Aim 3:** Conduct a pre-post trial to determine the feasibility and acceptability of the materials and using them in existing clinical workflows for their 1) impact on CBPC enrollment for CBPC-eligible individuals, including PLwD, and 2) end-user satisfaction.

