### 3. STUDY DESIGN

The study proposes to identify barriers to CBPC enrollment and develop ways to use the information from a valid, accurate data-drive algorithm to address barriers to enrollment. The study will 1) develop informational materials for CBPC team members that can be used to explain CBPC in a manner tailored to a patient's algorithm-identified risk profile (the intervention), and 2) pilot test whether the informational materials have an impact on CBPC uptake among patients who previously refused CBPC. This study will use a multi-methods design including data collection and pilot testing.

To achieve **Aim 1** focus groups and interviews with CBPC team members, VNS Health Total members, and FCP will be conducted to identify items important in accepting and refusing CBPC.

For **Aim 2** we will develop the intervention. The intervention is a set of information materials that address CBPC generally and challenges that CBPC can help manage. The materials will be tailored to patient needs based on their algorithm identified risk profile (e.g., disease progression, medication, and symptom management). The materials will be used by CBPC team members when introducing and describing the CBPC program to VNS Health Total members and FCP.

Aims 1 and 2 participants will not be offered any services. They will be asked about their understanding of palliative and why they chose not to accept it in the past. Their responses will be used to improve how palliative care services and programs are explained to others in the future.

For **Aim 3** we will compare intervention and usual care CBPC refusal rates and assess CBPC team member and FCP satisfaction with intervention materials using the End-User Satisfaction Tool. Because of the size of the CBPC clinical team and workflow structure, it is not feasible to randomize CBPC team members to intervention or control groups. As such, we will use a pre-post pilot clinical trial to test the feasibility and efficacy of the informational materials and process, compared to usual practice, on CBPC refusal rates. We will retrospectively examine CBPC refusal rates (CBPC refusals/CBPC eligible individuals) for a 6-month lookback

period prior to implementing the intervention (informational materials and process). We will compare this rate of refusal to the CBPC refusal rate for a 6-month period after implementing the intervention.

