**Table 1.**

Domain	Proposed measure (items)	Aims	Schedule	Participants
Demographic and Health Information	Age, sex, race, ethnicity, education level, perceived discrimination in healthcare encounters (FCP only), relationship to VNS Health Total member (FCP only), role on CBPC team (CBPC team members only), etc.	1-2	Baseline (Aim 1)	VNS Health Total members, FCP, CBPC team members, research/content experts (Aim 2 only)
	Age, sex, race, ethnicity, date of CBPC eligibility determination, date of CBPC refusal, diagnoses, triggering events	3	As extracted from electronic health record for pilot clinical trial analysis	VNS Health Total CBPC-eligible members
Knowledge of Palliative and Hospice Care	Palliative Care Knowledge Survey  additional questions on palliative care knowledge and attitudes 9/26/2025 8:41:00 PM	1-2	Baseline (Aim 1), following feedback on intervention materials (Aim 2)	VNS Health Total members, FCP
Intervention Development	Interview guides with questions about palliative care experiences, knowledge, barriers to participation in CBPC, including 5 rights framework (Aim 1); and user-centered design questions to solicit feedback on intervention materials (Aim 2)	1-2	1-time interview for Aim 1. 1-time think aloud session for Aim 2	VNS Health Total members, FCP, CBPC team members, research/content experts (Aim 2 only)
Intervention Feasibility and Acceptability	PC team member reports of use of intervention	3	1, 3, and 6 months into intervention delivery (Aim 3)	CBPC team members
	End-User Satisfaction Survey 	1, 3	Baseline (Aim 1); 1, 3, and 6 months into intervention delivery (Aim 3)	CBPC team members
Primary Endpoint	Number and rate of CBPC refusals (denominator=number of CBPC-eligible individuals)	3	As extracted from electronic health record for pilot clinical trial analysis	VNS Health Total CBPC-eligible members

**Data Collection Protocol.** Survey responses for Aims 1-3 will be collected in two ways: online or by telephone. Whenever possible, participants will be sent surveys to their preferred emails via REDCap, a password protected, HIPAA compliant data management system. Survey links will be unique to study

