## 4. SAMPLE SELECTION / DATA SOURCES

### **Aim 1. Identify barriers to CBPC enrollment.**

*Sample.* 10 CBPC team members and 25 VNS Health Total members and FCP.

*Inclusion Criteria.* VNS Health Total member who refused CBPC in the previous year or family care partner (including if they are paid for their caregiving) of a VNS Health Total member who refused CBPC services in the previous 12 months. VNS Health Total members and FCP must also be 18 years of age or older, English speaking and receive a score of 15 or higher on the one-minute animal fluency test. We will emphasize recruitment of FCP of PLwD. Although 75% of VNS Health Total CPBC participants have a dementia diagnosis, PLWD are not the only patient group served by the plan. As such, having a dementia diagnosis is not a requirement for participation. This will also allow us to compare refusal rates among PLWD and those without dementia in exploratory analyses.

CBPC team members must be a part of the VNS Health Total community-based palliative care team.

*Exclusion Criteria.* VNS Health Total members and FCP are excluded if they are: under the age of 18; do not speak English; FCP primary relationship to VNS Health Total member is employee or paid care partner (family members who are paid for their caregiving are eligible); VNS Health Total member or family member of FCP enrolled in VNS Health Total's CBPC in the previous 12 months.

PC team members are excluded if they are not a member of the palliative care team.

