### **Aim 3. Conduct a pre-post trial to determine the feasibility and acceptability of the materials and using them in existing clinical workflows for their impact on CBPC enrollment for PLwD and end-user satisfaction.**

*Sample.* Based on 2022 identification, eligibility, and refusal data, we anticipate 500 VNS Health Total members will be identified as eligible for CBPC during the study period (250 control, 250 intervention) and that

80 individuals will refuse CBPC during the pre-test/control period. Of these, 365 CBPC-eligible and 60 refusals are expected to be PLwD.

*Inclusion Criteria.* All VNS Health Total members who were identified as eligible for CBPC in the 6-month period prior to the introduction of the intervention (tailored informational materials about benefits of palliative care) and in the 6-month period following the introduction of the intervention.

*Exclusion Criteria.* VNS Health Total members who were not identified as potentially eligible for CBPC services by the 12-month mortality risk algorithm or who were identified by the algorithm as potentially eligible for CBPC services but determined by the clinical team to be ineligible for CBPC. At times, individuals are flagged by the algorithm as potentially eligible for CBPC, but upon further assessment by the palliative care team, it is determined that CBPC is not appropriate at this time. For example, someone may be flagged because they are over 90 years old and recently visited the emergency department. However, upon further assessment, the clinical team determines that they are highly functional and independent, their chronic conditions are well-managed, and the emergency room visit was for a minor head wound or something similar that did not greatly impact the individual's functional or health status.

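### The stated purpose is to test uptake among previous refusers, but Aim 3 analyses all eligible members and plans no separate estimate for previous refusers or for people with dementia

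*Combined protocol and SAP*

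**What the plan says.** Two general sections tie the pilot to people who have already declined the service. Section 1 (Purpose) says it will "pilot test whether the intervention has an impact on CBPC uptake among patients who previously refused CBPC". Section 3 (Study Design) says it will "pilot test whether the informational materials have an impact on CBPC uptake among patients who previously refused CBPC".

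The operative text for Aim 3 uses a wider population:

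- Section 2, Aim 3: "impact on CBPC enrollment for CBPC-eligible individuals, including PLwD".
- Section 3: the refusal rate is refusals divided by CBPC-eligible individuals.
- Table 1, primary endpoint: "Number and rate of CBPC refusals (denominator=number of CBPC-eligible individuals".
- Section 4, Aim 3 inclusion criteria: "All VNS Health Total members who were identified as eligible for CBPC in the 6-month period prior to the introduction of the intervention", and likewise for the 6 months after it. Prior refusal is neither required nor excluded.
- Sections 5 and 9: 500 eligible members, 250 per period. The power table rests on these numbers.

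Section 10 acknowledges that some Aim 3 members will have refused before and are being approached again.

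On dementia, the Aim 3 headings in Sections 4 and 10 describe the materials "for their impact on CBPC enrollment for PLwD and end-user satisfaction", without the other eligible members whom Section 2 includes. Sections 4 and 9 expect 365 of the 500 eligible members, and 60 refusals, to be PLwD. The one dementia analysis mentioned is in Section 4 under Aim 1: "This will also allow us to compare refusal rates among PLWD and those without dementia in exploratory analyses".

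**The concern.** A reader of Sections 1 and 3 expects the result to say whether the materials change the decision of people who had already declined. The planned contrast is the refusal rate among all eligible members before and after introduction, which mixes first offers with repeat offers. It could fall because first-time refusals fell while repeat refusals did not change, or the reverse. If the wording stays, a favourable overall result may be reported as an effect in previous refusers that was never estimated.

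The same applies, less sharply, to PLwD. The headings name them, but the overall contrast does not show whether refusal fell among them. The comparison mentioned under Aim 1 sets PLwD against members without dementia and does not say whether it is made by period.

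**Working it through.** **1. Which population does the power table describe?** Inputs from Section 9: 250 per period, pre-period rate 80/250 = 0.32, α = 0.05. The number of sides is not stated. With d = p1 − p2 and p̄ = (p1 + p2)/2, the two-sided formula with continuity correction is

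n0 = [1.96·√(2p̄(1−p̄)) + z_power·√(p1(1−p1) + p2(1−p2))]² / d²

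n = (n0/4)·[1 + √(1 + 4/(n0·d))]²

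For 0.32 against 0.206 at 80% power, n0 = 232.9 and n = 250.2. The other rows give 250.4 (0.199, 85%), 249.3 (0.190, 90%) and 251.9 (0.178, 95%). The table therefore reproduces at 250 per period and applies to all eligible members. It gives no power for previous refusers or for PLwD.

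**2. Is either group identified or analysed?**

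- *Previous refusers.* For Aim 3 members, Table 1 lists "date of CBPC eligibility determination, date of CBPC refusal, diagnoses, triggering events". It does not say whether refusals before the current eligibility episode are captured. Section 9 has no estimate for this group.
- *PLwD.* Diagnoses are on the same extraction list, so the group can be formed. Section 9 gives expected counts but no pre/post estimate within PLwD.

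**3. Precision of a pre/post risk difference.** With n per period, the 95% half-width is

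1.96·√[(p1(1−p1) + p2(1−p2))/n]

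| Population | n per period | Pre rate | No change | 11.4-point drop |
|---|---|---|---|---|
| All eligible | 250 | 0.320 | ±8.2 | ±7.7 |
| PLwD | 175 | 60/175 = 0.343 | ±9.9 | ±9.4 |
| PLwD, even split | 182.5 | 60/182.5 = 0.329 | ±9.6 | ±9.1 |
| PLwD | 190 | 60/190 = 0.316 | ±9.3 | ±8.7 |
| Previous refusers | 16 | 0.32 | ±32.3 | ±30.3 |
| Previous refusers | 40 | 0.32 | ±20.4 | ±19.1 |
| Previous refusers | 80 | 0.32 | ±14.5 | ±13.5 |
| Previous refusers | 125 | 0.32 | ±11.6 | ±10.8 |

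Half-widths are in percentage points.

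The PLwD rows assume that the 365 split about evenly between periods and that all 60 refusals fall in the pre-period.

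The previous-refuser rows are assumptions throughout. Section 5 gives about 160 refusers in 12 months, and 16, 40 and 80 are 10%, 25% and 50% of that. The figure 125 is half of the 250 eligible per period. The 32% rate is borrowed from the whole eligible population.

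**The case against.** The strongest reply is that this is loose background wording. Section 3 itself defines the rate over eligible individuals, every operative part of Aim 3 agrees, and nobody running the analysis could pick the wrong population. That stands: the primary analysis can be run as written, and no stated figure is wrong.

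On dementia, the headings in Sections 4 and 10 can be read as shortened forms of the Section 2 aim. PLwD are 365/500 = 73% of the expected sample, so the overall estimate mostly reflects them. It would therefore be wrong to say that dementia status goes unanalysed, since Section 4 announces an exploratory comparison. What remains is narrower: that comparison is not stated to be a pre/post contrast within PLwD.

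A reader might also infer from the table that the pilot is too small to say anything useful about previous refusers. The documents do not support that, because the answer turns on assumed inputs:

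- With 80 per period at 32%, the interval around an 11.4-point drop (±13.5) includes zero. With 125 (±10.8) it does not. The crossover is near 113 per period.
- With 80 per period, a 50% base rate and the plan's 35.6% relative reduction (0.50 to 0.322, a drop of 17.8 points), the half-width is ±15.0, which again excludes zero.
- Neither 80 nor 160 is a ceiling. The 160 is one year's refusers, while Sections 1 and 3 put no time limit on previous refusal.

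**Conclusion.** The mismatch is real and should be corrected. Sections 1 and 3 state a purpose about previous refusers, and the planned result describes all eligible members. Taken alone, that result cannot support a conclusion about people who had already refused, and it does not show whether refusal fell among PLwD.

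The point concerns the stated population and the missing estimates. It does not make the primary analysis invalid, and it does not show that a previous-refuser estimate would be uninformative.

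Under the split and count assumptions above, an estimate within PLwD would be only modestly less precise than the primary one: about ±9 to ±10 points against about ±8. For previous refusers, 16 to 125 per period at 32% with no change gives about ±32 to ±12 points. The documents supply neither the number nor the rate, so the true precision is unknown. Confidence is high for the wording mismatch and low for any previous-refuser precision figure.

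**What to change.** 1. Reconcile Sections 1 and 3 and the Aim 3 headings in Sections 4 and 10 with the Section 2 aim: all CBPC-eligible members, including PLwD. Add a sentence to Section 9 saying that the power table applies to all eligible members only. The cost is wording in four places and one sentence.

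2. In Section 9, add the pre/post risk difference in refusal with its 95% confidence interval within PLwD, labelled as exploratory estimation without a hypothesis test. The cost is one more estimate from diagnoses already on the extraction list.

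3. Only if the previous-refuser purpose is kept: define a prior-refusal flag with one stated lookback applied identically in both periods, and report the same exploratory estimate. First check that the Section 7 waiver covers the earlier dates. Its Aim 3 request covers identification, enrollment and refusal data, both for the before-and-after refusal rates and for factors associated with enrollment and refusal. The cost is an extract of earlier refusal dates and the waiver check, and refusals older than the lookback will be missed.

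The downside of steps 2 and 3 is that subgroup estimates are less precise than the primary estimate and should be reported as such. The primary endpoint and sample size do not change. If step 3 is not taken, step 1 alone removes the contradiction.

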### 2. SPECIFIC AIMS.

The specific Aims of the study are:

**Aim 1:** Engage FCPs and CBPC team members to identify barriers to CBPC. Aim 1 will incorporate the perspectives of 10 CBPC team members and 25 VNS Health Total members and FCPs of PLwD and those with other diagnoses who refused CBPC services.

**Aim 2:** Develop informational materials for CBPC team members to use when speaking with patients and FCPs about CBPC and process for tailoring information delivery based on patient's algorithm-identified risk profile. 10-15 persons from interested parties (CBPC team members, FCPs, content/research experts) will provide feedback on intervention materials. Most participants will be recruited from Aim 1 participants. Additional participants will be recruited as necessary.

**Aim 3:** Conduct a pre-post trial to determine the feasibility and acceptability of the materials and using them in existing clinical workflows for their 1) impact on CBPC enrollment for CBPC-eligible individuals, including PLwD, and 2) end-user satisfaction.

### 3. STUDY DESIGN

The study proposes to identify barriers to CBPC enrollment and develop ways to use the information from a valid, accurate data-drive algorithm to address barriers to enrollment. The study will 1) develop informational materials for CBPC team members that can be used to explain CBPC in a manner tailored to a patient's algorithm-identified risk profile (the intervention), and 2) pilot test whether the informational materials have an impact on CBPC uptake among patients who previously refused CBPC. This study will use a multi-methods design including data collection and pilot testing.

To achieve **Aim 1** focus groups and interviews with CBPC team members, VNS Health Total members, and FCP will be conducted to identify items important in accepting and refusing CBPC.

For **Aim 2** we will develop the intervention. The intervention is a set of information materials that address CBPC generally and challenges that CBPC can help manage. The materials will be tailored to patient needs based on their algorithm identified risk profile (e.g., disease progression, medication, and symptom management). The materials will be used by CBPC team members when introducing and describing the CBPC program to VNS Health Total members and FCP.

Aims 1 and 2 participants will not be offered any services. They will be asked about their understanding of palliative and why they chose not to accept it in the past. Their responses will be used to improve how palliative care services and programs are explained to others in the future.

For **Aim 3** we will compare intervention and usual care CBPC refusal rates and assess CBPC team member and FCP satisfaction with intervention materials using the End-User Satisfaction Tool. Because of the size of the CBPC clinical team and workflow structure, it is not feasible to randomize CBPC team members to intervention or control groups. As such, we will use a pre-post pilot clinical trial to test the feasibility and efficacy of the informational materials and process, compared to usual practice, on CBPC refusal rates. We will retrospectively examine CBPC refusal rates (CBPC refusals/CBPC eligible individuals) for a 6-month lookback

period prior to implementing the intervention (informational materials and process). We will compare this rate of refusal to the CBPC refusal rate for a 6-month period after implementing the intervention.

**Measurements.** All measures will be collected by study research team members via phone call or electronic survey. All participants will be assessed on the measures listed in Table 1 (see Appendix for more details). Aim 1 and 2 participants will be compensated \$75 each time they participate, up to \$150. Aim 3 CBPC team member participants will be compensated \$25 each time they complete the feasibility and acceptability surveys, up to \$75.

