### **Clinical Trial.**

*PC team member Recruitment.* All of the CBPC team members who present the CBPC program to CBPC-eligible individuals and FCP will be asked to use the informational materials developed as part of this project when speaking with VNS Health Total members and FCP about the CBPC program. We will work with the CBPC leadership to identify effective ways to engage CBPC team members in the intervention while minimizing potential burden. CBPC team members who deliver the intervention (i.e., use the informational materials when explaining CBPC to eligible individuals and their FCP) will be asked to complete fidelity, feasibility, and acceptability measures (e.g., End User Satisfaction Survey) at 1, 3, and 6 months into intervention implementation.

*VNS Health Total Member Recruitment.* We plan to conduct a pilot clinical trial of integrating tailored informational materials on the benefits of community-based palliative care for eligible persons based on their individualized profile as identified by a validated 12-month mortality risk algorithm. Based on recent VNS Health Total data regarding the number of individuals identified as eligible for palliative care, we expect to run the pilot clinical trial with 500 eligible individuals over an enrollment period of 12 months. This sample of 500 individuals included in the Inclusion Enrollment Table represents all individuals expected to be identified as eligible for palliative care during the study period (250 prior to intervention implementation and 250 following intervention implementation).

All data collection from VNS Health Total members for the pilot trial will be taken from existing electronic health records and remotely collected. For the pilot trial, the study team will not interact directly with palliative care-eligible individuals, or their FCP. All outcomes for VNS Health Total members will be captured through an existing data source (the VNS Health Total electronic record) under a waiver of informed consent (see below).

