## **7. REQUEST FOR WAIVER OF AUTHORIZATION**

In addition to obtaining consent from FCP, CBPC team member and research/content expert participants, we are requesting a waiver of consent and HIPAA authorization to access VNS Health Total member electronic records for the following reasons.

**Planning.** We will extract information about refusals of CBPC in the electronic health record such as the number of individuals who refused CBPC, their demographics, and health information (e.g., key diagnoses, triggering events that made them eligible for CBPC). Analyzing this information will allow us to improve information about risk for CBPC and who is refusing services so that we can create information materials and process 1) to support CBPC enrollment, particularly for PLwD and 2) that can be tested in other healthcare settings. As this extraction will involve several hundred records, including for deceased individuals, it is not possible to obtain this information without a waiver of authorization.

**Aims 1-2.** We request the waiver for VNS Health study staff to view electronic records of VNS Health Total members to identify VNS Health Total members and FCP who are potentially eligible to participate in Aims 1 and 2 of the study. It is not possible to identify potentially eligible members or FCP without the waiver of authorization.

**Aim 3.** We request the waiver for VNS Health study staff to view identification, enrollment, and refusal data. The information will be used to calculate CBPC refusal rates before and after intervention delivery and to analyze factors associated with CBPC enrollment and refusal in multivariable statistical modeling (described below).

A Request for Waiver of Authorization Form is included in the appendix of this application.

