### **Quantitative Analysis.**

For Aim 3, based on 2022 identification, eligibility, and refusal data, we anticipate 500 individuals will be identified as eligible for CBPC during the study period (250 control, 250 intervention) and that 80 individuals will refuse CBPC during the pre-test/control period. Of these, 365 CBPC-eligible and 60 refusals are expected to be PLwD.

We will use descriptive statistics to describe the sample. End-user satisfaction results will be reported as mean ratings for each item and across all items as a composite score. Results will also be reported by percentages of respondents by Likert scale level, as well as grouped by percent favorable and unfavorable. Percentage of clinicians finding the intervention to be feasible and acceptable and the proportion reporting using the informational materials will be calculated.

Additionally, we will determine the association between the intervention and reductions in refusal of CBPC among eligible individuals. We will use a pre/post design for this pilot clinical trial. For the pre-intervention measurement, we will calculate the number of palliative care services refusals among all palliative care-eligible VNS Health Total members (expected n=250) for a 6-month lookback period prior to introducing the informational materials into clinical practice. For the post-intervention measurement, after incorporating the informational materials into clinical practice, we will observe palliative care refusals prospectively for 6 months among all palliative care-eligible VNS Health Total members (expected n=250). We hypothesize that the number of refusals will decrease during the 6-month intervention period.

We assume we will see approximately 80 refusals among the 250 pre-intervention patients, for a refusal rate of  $80/250 = 0.32$  (or 32%) or  $H_0 = p_{pre} \geq p_{post}$ , where  $p_{pre}$  and  $p_{post}$  are the pre and post intervention CBPC refusal rates, respectively.

The table below show the post-intervention CBPC refusal rates we will be able to detect, for different power levels, assuming a total of 500 patients (250 pre, 250 post) a significance level  $\alpha = 0.05$ , and a pre-intervention CBPC refusal rate of 0.32.

Power	Pre-intervention CBPC refusal rate	Post-intervention CBPC refusal rate	Absolute rate reduction	Percent rate reduction
0.80	0.32	0.206	0.114	35.6%
0.85	0.32	0.199	0.121	37.8%
0.90	0.32	0.190	0.130	40.6%
0.95	0.32	0.178	0.142	44.4%

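### Aim 3's crude before/after refusal comparison is called a test of efficacy in Section 3, while Section 9 gives dates and case mix no role in it and never describes the multivariable model that Section 7 promises

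*Combined protocol and SAP*

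**What the plan says.** - **Design and claim.** Section 3 explains that team members cannot feasibly be randomized and continues: "we will use a pre-post pilot clinical trial to test the feasibility and efficacy of the informational materials and process". The comparison itself is one rate before and one after: "We will compare this rate of refusal to the CBPC refusal rate for a 6-month period after implementing the intervention".
- **Endpoint.** Table 1 defines the primary endpoint as "Number and rate of CBPC refusals (denominator=number of CBPC-eligible individuals").
- **Windows.** Section 4 (Aim 3) takes all members "identified as eligible for CBPC in the 6-month period prior to the introduction of the intervention" and those identified in the 6 months after it. Section 5 (Clinical Trial) puts the two together: "we expect to run the pilot clinical trial with 500 eligible individuals over an enrollment period of 12 months".
- **Data extracted.** For the Aim 3 analysis, Table 1 lists "Age, sex, race, ethnicity, date of CBPC eligibility determination, date of CBPC refusal, diagnoses, triggering events".
- **Analysis.** Section 9 (Quantitative Analysis) says "we will determine the association between the intervention and reductions in refusal of CBPC among eligible individuals". It gives a power table for 250 before and 250 after, but names no test, covariate or time term. Section 10 also speaks of association.
- **Promised model.** Section 7 justifies the Aim 3 waiver partly by the need "to analyze factors associated with CBPC enrollment and refusal in multivariable statistical modeling (described below"). No model is described in Section 9 or anywhere after it.

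**The concern.** The two groups differ in calendar time as well as in exposure to the materials. If refusal falls for another reason (season, a change in workflow, a different mix of triggering events), the planned contrast counts that fall as benefit. If refusal rises for another reason, the contrast hides benefit. Section 3 would then report the result as efficacy, which this design cannot support and which Sections 9 and 10 do not claim.

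The record fields that could at least address measured case mix will already be in hand. Because the model is not written down, covariates could be chosen after the results are seen, and part of the stated reason for the waiver has no matching analysis.

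**Working it through.** **Inputs (Section 9).** 250 members per period; refusal before 80/250 = 0.32; α = 0.05; planned rate after 0.206 (an 11.4-point reduction); 365 of 500 eligible members and 60 of 80 refusals are PLwD.

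**1. The plan's own power table.** Take a two-sided two-proportion test with pooled variance and continuity correction. For 0.32 v 0.206, the mean rate is 0.263. The null SE is √(2 × 0.263 × 0.737/250) = 0.0394. The alternative SE is √(0.32 × 0.68/250 + 0.206 × 0.794/250) = 0.0390. Power = Φ[(0.114 − 0.004 − 1.96 × 0.0394)/0.0390] = Φ(0.84) = 0.80. Exact binomial enumeration of this test gives 0.801, 0.851, 0.902 and 0.950 for the four rows, so the table reproduces. It is correct for a crude two-group comparison, and it treats the whole difference as intervention effect.

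**2. Margin for background change.** At 0.32 v 0.206 the 95% CI for the reduction is 0.114 ± 1.96 × 0.0390, or 3.7 to 19.1 points. A background fall of about 4 points (about 10 refusals in 250) would be enough to bring zero into it.

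**3. Effect of assumed drift, same test, exact enumeration.** The drift sizes are assumptions; the documents give none.

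| Scenario | Rate after | Chance of a significant reduction |
|---|---|---|
| No effect, no drift | 0.32 | 2% |
| No effect, 3-point fall | 0.29 | 9% |
| No effect, 5-point fall | 0.27 | 20% |
| No effect, 8-point fall | 0.24 | 47% |
| 11.4-point effect, no drift | 0.206 | 80% |
| 11.4-point effect, 3-point rise | 0.236 | 52% |
| 11.4-point effect, 5-point rise | 0.256 | 32% |

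**4. What the planned 12 months can separate.** Each calendar month falls in only one period. A model with 12 calendar months plus period has 13 columns but rank 12, so season and period cannot both be estimated. A linear trend can be fitted, but the SE of the period effect rises from 3.9 to 7.9 points, and power at 11.4 points is Φ(0.114/0.0789 − 1.96) = 0.30. (The same formula without trend gives 0.83; it exceeds the table's 0.80 because it has no continuity correction.) Nor does the trend remove season: with no effect, a half-year dip from 0.32 to 0.27 leaves a period effect of −5.0 points after the trend is fitted.

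**5. Case mix.** Assume the 365 PLwD split evenly, 182.5 per period. Refusal is then 60/182.5 = 32.9% in PLwD and 20/67.5 = 29.6% in others. Moving the PLwD share from 73% to 63% gives 0.63 × 0.329 + 0.37 × 0.296 = 0.317, a change of 0.3 point. The documents give no refusal rates for the other fields.

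**6. A year-earlier comparison.** Assume 250 members in each of three half-years before launch, all at 0.32. The SE of the pre/post change minus the same change one year earlier is √(3 × 0.32 × 0.68/250 + 0.206 × 0.794/250) = 0.057. Power at 11.4 points is Φ(0.114/0.0571 − 1.96) = 0.51. The cohort becomes 1,000 members instead of 500.

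**7. Members in both periods.** Section 10 says people offered the service before can become eligible again. If 10–30% of each period overlaps, with correlation 0.3–0.6 (both assumed), the true SE is 0.985 to 0.907 times the independent-groups SE. Ignoring the overlap is then mildly conservative.

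**The case against.** This is a pilot whose stated purpose is feasibility and acceptability. Randomization is ruled out with a reason, Sections 9 and 10 already say association, and *efficacy* is one word in one section. The drift sizes are hypothetical, and exposure to drift is a known limit of any uncontrolled before/after design. A season-and-trend analysis with about 51% power would settle little and would roughly double the number of records read under the waiver.

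Most of this stands. It makes the longer lookback optional, and it rules out treating the design itself as the fault. It does not answer the conflict between Section 3 and Sections 9 and 10 on what the primary endpoint will show, or the missing model.

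A reader might go further and infer that the plan ignores case mix altogether. The documents do not support that. Table 1 extracts the fields for the pilot analysis, Section 7 commits to some multivariable model, and Section 4 foresees an exploratory comparison by dementia status. The gap is confined to the contrast specified in Section 9. A reader might also infer that repeat members inflate false positives; under the overlap assumed above, the error is small and in the safe direction.

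**Conclusion.** The concern holds as a gap in the analysis plan and in the claim made from it. Section 3 promises more than an uncontrolled crude contrast can deliver, Section 9 gives the extracted dates and case-mix fields no part in that contrast, and the Section 7 model is absent. These points rest on the text alone.

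The size of any bias is unknown. The 20% figure for a 5-point fall (2% with no fall) shows sensitivity to an assumption and is not an estimate for this program. It would be wrong to conclude that the result will be biased: the documents contain no trend or seasonal data. It would also be wrong to expect adjustment to cure the problem. The only case-mix effect that can be calculated is about 0.3 point, assuming an even PLwD split, and no model fitted to these 12 months can remove season.

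**What to change.** 1. **Section 3:** replace *efficacy* with a preliminary, non-causal association, matching Sections 9 and 10.
2. **Section 9:** keep the crude comparison and name its test (two-sided, continuity-corrected two-proportion test, as the power table implies). Beside it, prespecify a period effect adjusted for age, sex, race/ethnicity, dementia diagnosis and triggering event, with sparse categories collapsed by a stated rule. Report it as a standardized risk difference with 95% CI. This supplies the model that Section 7 promises. State that it addresses measured case mix only, not season or trend, and may differ little from the crude estimate.
3. **Section 9:** show monthly refusal rates for the 12 months, from the dates already extracted.
4. **Optional, supportive only:** if comparable older records exist and the waiver and data use agreement allow it, extend the lookback to 18 months and compare the pre/post change with the same change one year earlier. State that this assumes a stable seasonal pattern and a linear trend.
5. **Optional:** member-clustered standard errors. These need a coded study ID, to be checked against the confidentiality terms in Section 11.

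Items 1 to 3 cost wording and a little analysis, with no new data. Item 4 needs no patient contact but adds about 500 members' records under wider waiver dates, for an SE of about 5.7 points and about 51% power at the planned effect.
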